8. SECONDARY STATISTICAL ANALYSES

8.1. Efficacy Analyses

8.1.1. Overview of Planned Efficacy Analyses

The secondary efficacy analyses will be based on the Intent-To-Treat population (of primary interest), and the subset ITT-2 to 6 years old population (supportive), unless otherwise specified.

Table 4 provides an overview of the planned efficacy analyses, with further details of data displays being presented in Appendix 14: List of Data Displays.

Table 4 Overview of Planned Efficacy Analyses

Endpoint	Absolute							Change from Baseline						
	Stats Analysis			Summary		Individual		Stats Analysis			Summary		Individual	
	T	F	L	T	F	F	L	T	F	L	T	F	F	L
Daily Reflective Total Ocular Symptom Scores				Y			Y				Y			Y
Mean Daily Reflective Total Ocular Symptom Scores over Each Week				Y			Y	Y			Y	Y		Y
Mean Daily rTOSS over the First 2 Weeks				Y			Y	Y			Y			Y
Mean Daily rTOSS over the 4 Weeks Treatment				Y			Y	Y			Y			Y
Overall Evaluation of Response to Therapy after the First 2 Weeks and 4 Weeks Treatment	Y			Y			Y							
Intranasal Finding Score by Anterior Rhinoscopy at the First 2 Weeks and 4 Weeks Treatment				Y			Y	Y			Y			Y
Rescue Loratadine Use (Mean Rescue-free Days) over the First 2 Weeks and 4 Weeks Treatment	Y			Y			Y							

NOTES :

- T = Table, F = Figure, L = Listing, Y = Yes display generated.
- Stats Analysis = Represents TFL related to any formal statistical analyses (i.e. modelling) conducted.
- Summary = Represents TFL related to any summaries (i.e. descriptive statistics) of the observed raw data.
- Individual = Represents FL related to any displays of individual subject observed raw data.

- All the tables will be presented by treatment group.

8.1.2. Planned Efficacy Statistical Analyses

Primary Statistical Analyses
Endpoint(s)

 • Overall evaluation of response to therapy (evaluated on a 7-point categorical scale) after the first 2 weeks treatment (day 15) • The mean change from baseline of study intranasal finding score by anterior rhinoscopy at the first 2 weeks treatment (day 15) • Mean change from baseline over the first 2 weeks treatment period in the daily reflective total ocular symptoms score (rTOSS) • Rescue loratadine use (mean rescue-free days) over the first 2 weeks treatment period • Overall evaluation of response to therapy after 4 weeks treatment period (day 29) • The mean change from baseline of intranasal finding score by anterior rhinoscopy at the end of treatment (day 29) • Mean change from baseline over the 4 weeks treatment period in the daily rTOSS • Rescue loratadine use (mean rescue-free days) over the entire 4 weeks treatment period
Model Specification

 • Overall evaluation of response to therapy (evaluated on a 7-point categorical scale) after the first 2 weeks treatment and 4 weeks will be analyzed using a logistic regression. • Terms fitted in the logistic regression model will be included: Treatment, classification of AR (IAR or PER), gender, age (as continuous variable). • For the Rescue loratadine use (mean rescue-free days) will be analyzed using an ANCOVA analysis • Terms fitted in the ANCOVA model will be included: 
 Fixed Categorical Covariates :Treatment, classification of AR (IAR or PER), gender Fixed Continuous Covariates : age • For the secondary endpoints of rTOSS and nasal finding score by anterior rhinoscopy will be analyzed using an ANCOVA analysis. • Terms fitted in the ANCOVA model will be included: 
 Fixed Categorical Covariates :Treatment, classification of AR (IAR or PER), gender Fixed Continuous Covariate : Baseline value of endpoint, age
Model Checking & Diagnostics

 • Refer to Appendix 12: Model Checking and Diagnostics for Statistical Analyses.
Model Results Presentation

 • For the ANCOVA model 
 ✓ LS means values for each treatment group will be presented with their associated standard errors. ✓ Estimated treatment differences along with corresponding 95% CIs and p-values will be presented for the treatment comparisons. • For the logistic regression model 
 ✓ Frequencies and percentages for each treatment group will be presented with each category. ✓ P-values will be presented for the treatment comparisons.

8.2. Safety Analyses

8.2.1. Overview of Planned Analyses

The safety analyses will be based on the Intent-To-Treat and subset Intent-To-Treat (2 to 6 years old) population, unless otherwise specified.

[Table 5](#) provides an overview of the planned analyses, with further details of data displays being presented in [Appendix 14](#): List of Data Displays.

Table 5 Overview of Planned Safety Analyses

Endpoint	Absolute				Change from Baseline			
	Summary		Individual		Summary		Individual	
	T	F	F	L	T	F	F	L
Exposure								
Extent of Exposure	Y			Y				
Adverse Events								
On-Treatment AEs	Y							
Post-Treatment AEs	Y							
AEs with Incidence Rate >3% in Any Treatment Group and More Common than Placebo During the Treatment Period	Y							
On-treatment Drug-Related AEs	Y			Y				
Relationship of Primary SOC, Preferred Term and Verbatim	Y							
All AEs				Y				
Serious Adverse Events								
SAEs	Y			Y				
Adverse Events Leading to Discontinuation of Study Treatment and Other Significant Adverse Events								
AEs Leading to Discontinuation of Study Treatment	Y			Y				
Nasal examination								
Nasal examination results by visit	Y			Y				
Shift from baseline	Y							
Abnormal nasal examination results				Y				
Laboratory Values								
Clinical Chemistry	Y			Y	Y			
Clinical Chemistry values outside the normal range	Y							

Endpoint	Absolute				Change from Baseline			
	Summary		Individual		Summary		Individual	
	T	F	F	L	T	F	F	L
Clinical Chemistry Shifts from Baseline to Endpoint	Y							
Subjects with at Least One Abnormal Value Post-Randomization in Chemistry				Y				
Haematology	Y			Y	Y			
Haematology values outside the normal range	Y							
Haematology Shifts from Baseline to Endpoint	Y							
Subjects with at Least One Abnormal Value Post-Randomization in Haematology				Y				
Routine Urinalysis	Y			Y				
Vital Signs								
Pulse Rate	Y				Y			
Systolic Blood Pressure	Y				Y			
Diastolic Blood Pressure	Y				Y			
Respiratory Rate	Y				Y			
Temperature	Y				Y			
12-Lead ECG								
QTc	Y				Y			
PR Interval	Y				Y			
Heart Rate	Y				Y			
ECG Findings	Y							
ECG Abnormal Clinically Significant				Y				
NOTES :								

 • T = Table, F = Figure, L = Listing, Y = Yes display generated. • Summary = Represents TFL related to any summaries (i.e. descriptive statistics) of the observed raw data. • Individual = Represents FL related to any displays of individual subject observed raw data. • All the tables will be presented by treatment group. 								

9. OTHER STATISTICAL ANALYSES

No other statistical analysis is planned.

11. APPENDICES

Section	Appendix
RAP Section 4 : Analysis Populations	
Section 11.1	Appendix 1 : Protocol Deviation Management and Definitions for Per Protocol Population
RAP Section 5 : General Considerations for Data Analyses & Data Handling Conventions	
Section 11.2	Appendix 2 : Time and Events
Section 11.3	Appendix 3 : Assessment Windows
Section 11.4	Appendix 4 : Treatment States & Phases
Section 11.5	Appendix 5 : Data Display Standards & Handling Conventions 
 • Study Treatment & Sub-group Display Descriptors • Baseline Definitions & Derivations • Reporting Process & Standards
Section 11.6	Appendix 6 : Derived and Transformed Data 
 • General, Study Population & Safety • Efficacy
Section 11.7	Appendix 7 : Premature Withdrawals & Handling of Missing Data 
 • Premature Withdrawals • Handling of Missing Data
Section 11.8	Appendix 8 : Values of Potential Clinical Importance
Section 11.9	Appendix 9 : Multicentre Studies
Section 11.10	Appendix 10 : Examination of Covariates and Subgroups
Section 11.11	Appendix 11 : Multiple Comparisons and Multiplicity
Section 11.12	Appendix 12 : Model Checking and Diagnostics for Statistical Analyses
Other RAP Appendices	
Section 11.13	Appendix 13 : Abbreviations & Trade Marks
Section 11.14	Appendix 14 : List of Data Displays
Section 11.15	Appendix 15 : Example Mock Shells for Data Displays

11.1. Appendix 1: Protocol Deviation Management and Definitions for Per Protocol Population

11.1.1. Exclusions from Per Protocol Population

Protocol deviations identified here are those considered to affect the primary outcome of the study. All decisions on whether to exclude a subject from analysis will be made prior to breaking the blind, with the exception of subjects receiving incorrect treatment container. If, after breaking the blind, the container was found to have contained the correct randomised treatment, no data will be excluded from analyses.

11.1.2. Exclusions of Data from Per Protocol Analyses

Subjects with full protocol deviations identified below will be excluded from the PP population. Subjects with partial protocol deviations will generally be included in the PP population but have data excluded from PP analyses from the time of the deviation onwards.

11.1.2.1 Inclusion/exclusion/randomisation Criteria Deviations

Failure of criteria will be considered a full protocol deviation as detailed in [Table 6](#):

Table 6 Inclusion/exclusion/randomisation criteria deviations considered to affect the primary outcome

Reason for exclusion	Full protocol deviation considered to affect primary outcome
Inclusion criterion	
Informed consent	Yes
Outpatient	No
Gender	No
Age	No
Diagnosis of AR	Yes
Exposure	No
Ability to Comply with Procedures	Yes
Exclusion criterion	
Concomitant Medical Conditions	depends
Concomitant Medication	depends
Subjects Will Travel More Than 48 Hours During the Study may Cause the Change of Allergen	No
Investigators or Sub-investigators Consider that a Subject is Not Eligible	Yes
Randomisation criterion	
On the morning of Visit 2, subjects must have nasal or/and ocular	Yes

Reason for exclusion	Full protocol deviation considered to affect primary outcome
symptoms	
Average of the last 8 rTNSS assessments (4 AM assessments, 4 PM assessments) over the consecutive four 24-hours periods prior to randomization must be ≥ 6	Yes
Average of the 8 reflective nasal symptom assessments for congestion (4 AM assessments, 4 PM assessments) over the consecutive four 24-hour periods prior to randomization must be ≥ 2	Yes

11.2. Appendix 2: Time & Events

11.2.1. Protocol Defined Time & Events¹

Procedure	Visit Number					Early withdraw	Follow up
	1	2	3	4	5		
	Study Day						
Visit window (of days)	-4 to -14	1	8±2	15±2	29±2		5±2 days after V5 or EW
Informed consent ²	X						
Subject number assignment	X						
Medical history	X						
Verification of inclusion/exclusion criteria	X						
Skin testing / serum-specific IgE test (if not done within 12 months of visit 1)	X						
Clinical laboratory tests[Randomisation] if applicable	X				X	X	
12-Lead electrocardiogram	X				X	X	
Verification of randomized criteria		X					
Randomization number assignment		X					
Dispense double-blind study drug		X					
Dispense rescue loratadine		X	X ³	X ³			
Nasal spray technique education		X	X	X			
Collect study drug					X	X	
Review screening diary ⁴		X					
Review medical problem/medication diary ⁵		X	X	X	X	X	
Compliance assessment			X	X	X	X	
Review treatment diary ⁴			X	X	X	X	
Anterior rhinoscopy		X	X	X	X	X	
Investigator assess overall response to therapy				X	X	X	
Vital Signs	X				X	X	
Nasal examination	X	X	X	X	X	X	
Physical examination	X				X	X	
AE/SAE review	X ⁶	←-----→				X	X

Procedure	Visit Number					Early withdraw	Follow up
	1	2	3	4	5		
	Study Day						
Visit window (of days)	-4 to -14	1	8±2	15±2	29±2		5±2 days after V5 or EW
Concomitant medication review		←=====→				X	X

1. Parent/guardian will record the symptom diary instead of subjects for all ages. The involvement of the parent/guardian in assessing and rating rhinitis symptoms may vary per subject. While it may not always be possible, the preference is for a consistent level of parent/guardian involvement throughout the study.
2. Informed Consent must be obtained prior to performing any Visit 1 procedures.
3. The dispense will depends on as needed.
4. The diary collects rTNSS, rTOSS, rescue usage and study medication usage.
5. The diary collect any medical problem (other than AR) and any medications used.
6. Serious AEs will be recorded from the time the consent form is signed until the follow-up visit. All AEs will be recorded from the start of study treatment until the follow-up visit.

11.3. Appendix 3: Assessment Windows

Assessment windows for the scheduled study visits are as follows:

Visit 1 Screening (4 to 14 days prior to randomization)

Visit 2 Randomization (Day 1)

Visit 3 (8 ± 2 days after Visit 2, Week 1)

Visit 4 (15 ± 2 days after Visit 2, Week 2)

Visit 5 (29 ± 2 days after Visit 2, Week 4)

Individual assessments collected outside of the assessment window of scheduled visits will be included in the analysis without adjustment. If multiple assessments were collected within the same assessment window, the last valid value prior to randomization was used as the baseline value and the first valid value was used for all post-randomization visits.

will still be included in all ITT analyses.

11.4. Appendix 4: Treatment States and Phases

11.4.1. Treatment Phases

Assessments and events will be classified according to the time of occurrence relative to study treatment, unless otherwise specified.

Treatment Phase	Definition
Pre-Treatment	Date < Study Treatment Start Date
On-Treatment	Study Treatment Start Date ≤ Date ≤ Study Treatment Stop Date + 1
Post-Treatment	Date ≥ Study Treatment Stop Date + 2

NOTES:

- If the study treatment stop date is missing then the assessment will be considered to be On-Treatment

11.4.2. Treatment States

Assessments and events will be classified according to time of occurrence relative to the start and/or stop date of the study treatment.

11.4.2.1. Treatment States for Concomitant Medications Data

Treatment State	Definition
Pre-Treatment	Medication start date < Study Treatment Start Date
On-Treatment	Medication start date ≤ Study Treatment Stop Date and Medication stop date ≥ Study Treatment Start Date
Post-Treatment	Medication stop date > Study Treatment Stop Date

NOTES:

- A medication will be classed in every period of the study in which it was taken.
- For medications with partial start and stop dates or missing start/stop dates, the medication will be classed in every period of the study in which it could have been taken.
- If the study treatment stop date is missing then the medication will be considered to be On-Treatment.
- The answers to the questions "Taken Prior to Study?" and "Ongoing?" which are recorded on the eCRF will also be taken into consideration to determine if the medication was started pre-treatment or continued post-treatment. In each case, should the answers suggest a different classification than the dates, the medication will be summarised in all possible classifications (pre/on/post) in which it could conceivably have been taken.

11.4.2.2. Treatment States for AE Data

Treatment State	Definition
Pre-Treatment	AE Start Date < Study Treatment Start Date
On-Treatment	Study Treatment Start Date ≤ AE Start Date ≤ Study Treatment Stop + 1
Post-Treatment	AE Start Date > Study Treatment Stop Date + 1
Onset Time Since 1 st Dose (Days)	If Treatment Start Date > AE Onset Date = AE Onset Date - Treatment Start Date; If Treatment Start Date ≤ AE Onset Date = AE Onset Date - Treatment Start Date + 1 Missing otherwise.

Treatment State	Definition
Duration (Days)	AE Resolution Date - AE Onset Date + 1
Drug-related	If relationship is marked 'YES' on Inform/CRF OR value is missing.

NOTES:

- If the AE onset date is missing or partial then the AE will be considered on-treatment unless there is evidence to the contrary (e.g. the month of the onset date is present and is less than the month of the first dose of study treatment).
- AEs reported by subjects who did not receive treatment will be considered pre-treatment.
- Any SAEs for screen failures, run-in failures or subjects who were randomised but did not receive treatment will be classified as pre-treatment SAEs.

11.5. Appendix 5: Data Display Standards & Handling Conventions

11.5.1. Study Treatment & Sub-group Display Descriptors

Treatment Group Descriptions			
RandAll NG		Data Displays for Reporting	
Code	Description	Description	Order ^[1]
A	GW685698 55 µg QD	FF 55 µg QD	2
B	GW685698 110 µg QD	FF 110 µg QD	3
D	Pooled GW685698 Groups	FF 55/110 µg QD	4
P	Placebo	Placebo	1

NOTES:

- Order represents treatments being presented in TFL, as appropriate.

11.5.2. Baseline Definition & Derivations

11.5.2.1. Baseline Definitions

For all endpoints (except diary card) the baseline value will be the latest pre-dose assessment.

The baseline period for diary card endpoints is defined as 4 days prior to randomization, including the AM symptom assessment on the randomization (i.e., treatment initiation) date.

11.5.2.2. Derivations and Handling of Missing Baseline Data

Definition	Reporting Details
Change from Baseline	= Post-Dose Visit Value – Baseline Value

NOTES :

- Unless otherwise specified, the baseline definitions specified in Section 11.5.2.1 Baseline Definitions will be used for derivations for endpoints / parameters and indicated on summaries and listings.
- If either the baseline or on-treatment value is missing then the change from baseline will be set to missing.
- The change from baseline will not be calculated for baseline records or records prior to baseline.

11.5.3. Reporting Process & Standards

Reporting Process	
Software	

 The version 9.2 of SAS software will be used. 	
Reporting Area	
HARP Server	Not applicable since this is a CRO study
HARP Area	Not applicable since this is a CRO study

Reporting Process	
QC Spreadsheet	Not applicable since this is a CRO study
Analysis Datasets	

 Analysis datasets will be created according to GSK A&R dataset standards. 	
Generation of RTF Files	

 RTF and PDF files will be generated. 	
Reporting Standards	
General	

 The current GSK Integrated Data Standards Library (IDSL) will be applied for reporting, unless otherwise stated: 
 4.03 to 4.23: General Principles 5.01 to 5.08: Principles Related to Data Listings 6.01 to 6.11: Principles Related to Summary Tables 7.01 to 7.13: Principles Related to Graphics 	
Formats	

 All data will be reported according to the actual treatment the subject received unless otherwise stated. GSK IDSL Statistical Principles (5.03 & 6.06.3) for decimal places (DP's) will be adopted for reporting of data based on the raw data collected. Numeric data will be reported at the precision collected on the eCRF. The reported precision from non eCRF sources will follow the IDSL statistical principles but may be adjusted to a clinically interpretable number of DP's. 	
Planned and Actual Time	

 Reporting for tables, figures and formal statistical analyses : 
 Planned time relative to dosing will be used in figures, summaries, statistical analyses and calculation of any derived parameters, unless otherwise stated. The impact of any major deviation from the planned assessment times and/or scheduled visit days on the analyses and interpretation of the results will be assessed as appropriate. Reporting for Data Listings: 
 Planned and actual time relative to study drug dosing will be shown in listings (Refer to IDSL Statistical Principle 5.05.1). Unscheduled or unplanned readings will be presented within the subject's listings. Visits outside the protocol defined time-windows (i.e. recorded as protocol deviations) will be included in listings but omitted from figures, summaries and statistical analyses. 	
Unscheduled Visits	

 Unscheduled visits will not be included in summary tables. Unscheduled visits will not be included in figures. All unscheduled visits will be included in listings. 	
Descriptive Summary Statistics	
Continuous Data	Refer to IDSL Statistical Principle 6.06.1
Categorical Data	N, n, frequency, %

Reporting Standards
Graphical Displays

• Refer to IDSL Statistical Principals 7.01 to 7.13.

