11.6.3. Safety

Extent of Exposure

- Number of days of exposure to study drug will be calculated based on the formula:
Duration of Exposure in Days = (Treatment Stop Date – Treatment Start Date) + 1
- If a subject’s **treatment** stop date is missing it will be assumed to be date of the study discontinuation/completion. If the study discontinuation/completion date is also missing then the extent of exposure will be set to missing.
- If a subject’s **treatment** start date is missing then it will be assumed to be their Day 1 visit date.

Laboratory Parameters

- The baseline value for a parameter will be the most recent recorded value for that parameter before dosing on Day 1.
- Laboratory data values will be classified as ‘low’, ‘normal’ or ‘high’ with reference to normal ranges.
- Laboratory data (haematology, chemistry, and urinalysis) will be collected during Visit 1 (Screening) and Visit 5 (Week 4) / Early Withdrawal. The laboratory data will be summarized by visit. The number and percentage of subjects with laboratory values outside the normal range will be summarized by study visit for each laboratory analyte.
- Shift tables will summarize post-treatment flag values [low (L), normal (N), or high (H)] for each analyte, relative to their baseline flag values. Laboratory values are flagged as “low” if they are less than the lower limit of the normal range, “normal” if they are within the normal range and “high” if they are above the upper limit of the normal range. Baseline is defined as the last laboratory values captured prior to randomization [i.e., at Visit 1 or, where applicable, a repeat assessment performed prior to administration of the first dose of study medication at Visit 2

Laboratory Parameters

(Randomization, Day 1)]. The endpoint is defined as the first post-treatment value (i.e. laboratory value collected at Visit 5 (Week 4) or withdrawal visit). Shift from baseline to endpoint (Week 4 / discontinuation) in laboratory value is categorized, for each laboratory analyte, as follows:

To High	L to H, N to H
To Normal or No Change	L to N, H to N, L to L, N to N, H to H
To Low	N to L, H to L.

The number of subjects in each category will be summarized for each laboratory analyte.

- All laboratory values for subjects with at least one post-treatment laboratory value (Including repeat assessments) outside the normal range will be listed.

Nasal Examinations

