- The baseline value for a nasal examination endpoint will be the most recent recorded value for that endpoint before dosing on Day 1.
- Nasal examinations will be collected during Visits 1-5 or Early Withdrawal. Summary statistics for mucosa, septum, secretions, nasal patency, size of any polyps and ulcers will be provided at Visit 1-5 or Early Withdrawal.
- A summary of change from baseline in nasal examinations at endpoint (Vsit5/Early Withdrawal) will be made.

Vital Signs

- The baseline value for a vital sign endpoint will be the most recent recorded value for that endpoint before dosing on Day 1.
- Vital signs will be collected during Visit 1 (Screening) and Visit 5 (Week 4)/Early Withdrawal. Summary statistics for systolic blood pressure (mmHg), diastolic blood pressure (mmHg), heart rate (beats/min), temperature (°C), and respiratory rate (breaths/min) will be provided at baseline and Visit 5 or Early Withdrawal.
- A summary of change from baseline in vital signs at endpoint (Vsit5/Early Withdrawal) will be made.

12-Lead ECG

- The baseline value for an ECG endpoint will be the most recent recorded value for that endpoint before dosing on Day 1.
- Twelve-lead ECGs will be performed at Visit 1 (Screening) and Visit 5 (Week 4)/Early Withdrawal. ECG results of "normal", "abnormal, not clinically significant (NCS)", and "abnormal, clinically significant (CS)" will be summarized at baseline and Visit 5 or Early Withdrawal.
- A listing of subjects with abnormal clinically significant ECG evaluations and/or clinically significant change(s) in ECG evaluations will be provided.

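### SAP 11.3 keeps out-of-window assessments in the analysis, SAP 11.5.3 drops out-of-window visits from it, and neither section says which prevails

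*SAP*

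**What the plan says.** Two places in the SAP deal with scheduled visits held early or late.

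- **SAP 11.3 (Assessment Windows)** lists the visit windows and then states: "Individual assessments collected outside of the assessment window of scheduled visits will be included in the analysis without adjustment". The section closes with an incomplete line. Its subject is missing, but it speaks of something remaining in all ITT analyses.
- **SAP 11.5.3 (Reporting Process & Standards, Planned and Actual Time)** states, under the sub-heading for data listings: "Visits outside the protocol defined time-windows (i.e. recorded as protocol deviations) will be included in listings but omitted from figures, summaries and statistical analyses". The bullet for tables, figures and formal analyses in the same section says that "The impact of any major deviation from the planned assessment times and/or scheduled visit days on the analyses" and on interpretation will be assessed as appropriate.

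The analyses concerned are described elsewhere. SAP 8.1.1 says: "The secondary efficacy analyses will be based on the Intent-To-Treat population (of primary interest"). SAP 8.1.2 includes visit-based endpoints such as "The mean change from baseline of intranasal finding score by anterior rhinoscopy at the end of treatment (day 29"). SAP 11.6.3 defines the laboratory endpoint by visit: "The endpoint is defined as the first post-treatment value (i.e. laboratory value collected at Visit 5 (Week 4) or withdrawal visit"). It treats vital signs in the same way: "A summary of change from baseline in vital signs at endpoint (Vsit5/Early Withdrawal) will be made".

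**The concern.** The two rules give opposite instructions for the same record, so a programmer must choose one, and the SAP gives no basis for choosing.

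The 11.5.3 rule would remove data from analyses described as intent-to-treat. At Visits 3 to 5 the reason for removal, visit timing, arises after randomisation and could be related to symptoms or tolerability. The loss is greatest for laboratory tests, vital signs and ECG. The Time and Events Table schedules these only at Visit 1 and at Visit 5 or early withdrawal, so omitting an out-of-window Visit 5 takes away a completer's only scheduled post-baseline value.

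If the choice is left open past unblinding, it could be made with the results in view.

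**Working it through.** The plan has no figure to reproduce here. The check compares the texts and then counts what depends on the rule.

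**1. Is the conflict only a matter of differently defined windows?** Protocol Table 2 gives windows in study days. SAP 11.3 gives them as days after Visit 2, for example "Visit 4 (15 ± 2 days after Visit 2, Week 2"). SAP 11.6.1 counts the randomisation date as Day 1, so a literal reading of 11.3 falls one day later:

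| Visit | Protocol study days | SAP 11.3 read literally |
|---|---|---|
| 3 | 6–10 | 7–11 |
| 4 | 13–17 | 14–18 |
| 5 | 27–31 | 28–32 |

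A Visit 4 on study day 20 is outside both versions. It is analysed under 11.3 and omitted under 11.5.3, so the conflict does not come from the one-day shift.

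**2. Is precedence stated anywhere?** SAP 4, 11.1, 11.6 and 11.7 and protocol section 9 contain no such rule. The qualifier in 11.5.3 that allows for exceptions stated elsewhere belongs to the planned-time bullet, not to the omission sentence. The unscheduled-visit rules in 11.5.3 concern a different kind of visit.

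**3. What depends on the rule?**

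- Secondary efficacy endpoints (SAP 2.2): overall response at Days 15 and 29 (2) + rhinoscopy at Days 15 and 29 (2) = 4 of 9.
- Efficacy tables (SAP 11.14.6): overall response 2.11–2.12 (2) + rhinoscopy 2.13–2.16 (4) = 6 of 22.
- Safety tables (SAP 11.14.8): laboratory 3.20–3.39 (20) + nasal examination 3.40–3.43 (4) + vital signs 3.44–3.47 (4) + ECG 3.48–3.53 (6) = 34 of 53.
- Together 6 + 34 = 40 of 31 + 22 + 53 = 106 planned tables. These are 20 displays, each produced for the ITT and the subset ITT populations.
- Read literally, 11.5.3 also covers Tables 1.05 and 1.06 (number of subjects at each visit), which makes 42.

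The diary endpoints do not enter, because SAP 11.6.4 takes the randomisation date as their reference.

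**4. What would it cost in precision?** The out-of-window share is not in the documents, so a range is assumed. Starting from the planned 100 evaluable per arm, with a share f omitted, the 95% CI half-width for a difference in means grows by the factor √(1/(1−f)):

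| Assumed f | n per arm | Widening |
|---|---|---|
| 5% | 95 | √(100/95) − 1 = 2.6% |
| 10% | 90 | √(100/90) − 1 = 5.4% |
| 20% | 80 | √(100/80) − 1 = 11.8% |

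This covers precision only. Bias from timing-related omission cannot be calculated from the documents.

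**The case against.** The strongest reply is that the intended rule can be inferred. The omission sentence sits under the data-listings sub-heading, and the unfinished line in 11.3 leans towards keeping the data in ITT analyses. The per-protocol deviation tables in SAP 11.1 do not name visit timing as a reason for exclusion, so it would be odd to exclude on that ground from ITT. All of this is sound and supports inclusion. It does not settle the matter: the 11.5.3 sentence expressly reaches summaries and statistical analyses, and the 11.3 line is incomplete. The bullet on assessing the impact of timing deviations is weaker evidence, since omitting visits also has an impact that could be assessed.

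A second reply is that little is at stake. The study is descriptive, the primary endpoint is untouched, and a count of tables does not measure an effect on results. This is right and limits the weight of the point. A table depends on the rule even if every visit turns out to be in window.

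A third is that 11.3 speaks of assessments and 11.5.3 of visits. That does not separate them, because 11.3 refers to the windows of scheduled visits, and an out-of-window visit yields out-of-window assessments.

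**Conclusion.** The SAP contradicts itself, and the text needs correcting before database freeze. The conflict is confined to visit-based data: four of nine secondary efficacy endpoints and the by-visit safety summaries. The primary endpoint, rTOSS, rescue-free days and adverse events are unaffected.

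For Visits 3 to 5, applying 11.5.3 would remove only that visit's data; the child's other visits would stay in. Visit 1 is an exception. Its window is Day −4 to −14, and it supplies the baseline for laboratory tests, vital signs and ECG. If an out-of-window Visit 1 were omitted and no later pre-dose value existed, SAP 11.5.2.2 would set the change from baseline to missing.

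Inclusion is the better-supported rule. It fits the ITT basis of the secondary analyses. Protocol 9.3.1 and 9.4 contain no window-based exclusion, and SAP 2.1 declares no change from the protocol's analysis, so omission would be an undeclared departure. The number of records affected is unknown, and the precision figures rest on assumed shares.

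**What to change.** Delete the out-of-window sentence from SAP 11.5.3 and replace it with, for example: *Assessments outside the protocol-defined windows are listed with their actual study day and analysed under their nominal visit (see 11.3).*

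In SAP 11.3, complete or remove the unfinished closing line. As an editorial correction, restate the windows as Study Day 8±2, 15±2 and 29±2 with Visit 2 as Day 1, to match the protocol. That correction does not decide who enters the Day 15 or Day 29 analyses; it affects only the choice among several assessments falling in one window.

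The SAP synopsis already requires decisions on the final analysis to be made before database freeze, and this should be one of them. The cost is SAP wording only, with no new data and no protocol amendment.
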